8.2.2. Exclusion Criteria

Patients meeting any of the following criteria will not be included in the study:

1. Subjects with participation in studies involving investigational drugs within 24 months before the index dates.

8.3. Variables

Variables are described in the [Table 1](#) below. If more than one measurement is taken during the baseline period, the most recent measurement to index date will be recorded to eCRF system.

Table 1. Variables of interests

Variable	Role	Assessment Period	Output	Data Source(s)	Operational Definition
Age at ATTR-CM diagnosis	Patient Baseline Characteristics, Secondary Objective	Baseline Assessment Period	Continuous	Electronic health records	Age will be calculated based on date of birth
Age at tafamidis start	Patient Baseline Characteristics, Secondary Objective	Baseline Assessment Period	Continuous	Electronic health records	Age will be calculated based on date of birth
Gender (M/F)	Patient Baseline Characteristics, Secondary Objective	Baseline Assessment Period	Nominal	Electronic health records or physical patient file	Male or female
Height (cm)	Patient Baseline Characteristics, Secondary Objective	Baseline Assessment Period	Continuous	Electronic health records or physical patient file	Cm, (100-200)
Weight (kg)	Patient Baseline Characteristics, Secondary Objective	Baseline Assessment Period	Continuous	Electronic health records or physical patient file	Kg, (30-150)
BMI (Body Mass Index)	Patient Baseline Characteristics, Secondary Objective	Baseline Assessment Period	Continuous	Electronic health records or physical patient file	Categorized as underweight (<18.5) normal (18.0–24.9 kg/m ²), overweight (25.0–29.9 kg/m ²), or obesity (≥30 kg/m ²) (15-45)
Body Surface Area (automatic)	Patient Baseline Characteristics,	Baseline Assessment Period	Continuous	Electronic health records	Calculated with height and weight

	Secondary Objective			or physical patient file	
Hypertension (history of diagnosis:	Patient Baseline Comorbidities, Secondary Objective	Baseline Assessment Period	Nominal	Electronic health records or physical patient file	History of hypertension (yes/no/missing) as documented in the source data
Diabetes Mellitus (history of diagnosis: Yes; or not: No)	Patient Baseline Comorbidities, Secondary Objective	Baseline Assessment Period	Nominal	Electronic health records or physical patient file	History of diabetes mellitus (yes/no/missing) as documented in the source data
Hyperlipidemia ^a	Patient Baseline Comorbidities, Secondary Objective	Baseline Assessment Period	Nominal	Electronic health records or physical patient file	History of hyperlipidemia (yes/no/missing) as documented in the source data
Coronary Artery Disease	Patient Baseline Comorbidities, Secondary Objective	Baseline Assessment Period	Nominal	Electronic health records or physical patient file	History of coronary artery disease (yes/no/missing) as documented in the source data
Heart Failure Stages	Patient Baseline Comorbidities, Secondary Objective	Baseline Assessment Period	Ordinal	Electronic health records or physical patient file	0-None 1-HFrEF (Heart Failure with preserved ejection fraction) 2-HFmrEF (Heart Failure with mildly reduced ejection fraction) 3-HFrEF (Heart Failure with reduced ejection fraction)
NYHA Class	Patient Baseline Comorbidities, Functional outcome, Secondary Objective	Baseline, Follow up Assessment Period	Ordinal	Electronic health records or physical patient file	A clinical assessment of a patient's cardiac disease and functional ability based on symptoms. Class 1-2-3-4

Chronic Obstructive Pulmonary Disease (COPD)	Patient Baseline Comorbidities, Secondary Objective	Baseline Assessment Period	Nominal	Electronic health records or physical patient file	History of COPD (yes/no/missing) as documented in the source data
Atrial Fibrillation (AF)	Patient Baseline Comorbidities, Secondary Objective	Baseline Assessment Period	Nominal	Electronic health records or physical patient file	History of atrial fibrillation (yes/no/missing) as documented in the source data
Aortic Stenosis	Patient Baseline Comorbidities, Secondary Objective	Baseline Assessment Period	Ordinal	Electronic health records or physical patient file	History of atrial fibrillation (yes/no/missing) as documented in the source data 0-None 1-Mild 2-Moderate 3-Severe
History of Surgical Aortic Valve Replacement (SAVR) or Transcatheter Aortic Valve Implantation (TAVI)	Patient Baseline Comorbidities, Secondary Objective	Baseline Assessment Period	Nominal	Electronic health records or physical patient file	History of SAVR or TAVI (yes/no/missing) as documented in the source data
Carpal Tunnel Syndrome	Extracardiac Red Flag, Secondary Objective	Baseline Assessment Period	Nominal	Electronic health records or physical patient file	History of Carpal Tunnel Syndrome (yes/no/missing) as documented in the source data
Peripheral Neuropathy	Extracardiac Red Flag, Secondary Objective	Baseline Assessment Period	Nominal	Electronic health records or physical patient file	History of peripheral neuropathy (yes/no/missing) as documented in the source data
Lumbar Stenosis	Extracardiac Red Flag, Secondary Objective	Baseline Assessment Period	Nominal	Electronic health records or physical patient file	History of lumbar stenosis (yes/no/missing)

						as documented in the source data
Pacemaker history	Patient Baseline Comorbidities, Secondary Objective	Baseline Assessment Period	Nominal	Electronic health records or physical patient file	History of pacemaker implantation (yes/no/missing) as documented in the source data	
Co- medications	Patient Baseline and Follow up Co- medications, Secondary Objective	Baseline, Follow up Assessment Period	Nominal	Electronic health records or physical patient file	Record of treatments used at the assessment timepoint (1: diuretics, 2: beta blockers 3: renin angiotensin axis inhibitors 4: anticoagulants 5: other)	
Hemoglobin	Patient Baseline Laboratory Parameters, Secondary Objective	Baseline Assessment Period	Continuous	Electronic health records or physical patient file	As recorded in the source data g/dL, (5-20)	
Creatinine	Extracardiac Red Flag, Functional Outcome, Secondary Objective	Baseline, Follow up Assessment Period	Continuous	Electronic health records or physical patient file	As recorded in the source data mg/dL, (0.3-10)	
eGFR (glomerular filtration rate)	Extracardiac Red Flag, Functional Outcome, Secondary Objective	Baseline, Follow up Assessment Period	Continuous	Electronic health records or physical patient file	Automatic calculation with creatinine	
Sodium	Patient Baseline Laboratory Parameters, Secondary Objective	Baseline Assessment Period	Continuous	Electronic health records or physical patient file	As recorded in the source data mmol/L, (100-200)	
Potassium	Patient Baseline Laboratory	Baseline Assessment Period	Continuous	Electronic health records	As recorded in the source data mmol/L, (2-10)	

	Parameters, Secondary Objective			or physical patient file	
ALT (Alanine transaminase) U/L	Patient Baseline Laboratory Parameters, Secondary Objective	Baseline Assessment Period	Continuous	Electronic health records or physical patient file	As recorded in the source data U/L (1-1000)
AST (Aspartate aminotransferase)	Patient Baseline Laboratory Parameters, Secondary Objective	Baseline Assessment Period	Continuous	Electronic health records or physical patient file	As recorded in the source data U/L, (5-1000)
Albumin	Patient Baseline Laboratory Parameters, Secondary Objective	Baseline Assessment Period	Continuous	Electronic health records or physical patient file	As recorded in the source data g/L, (10-200)
Modified BMI	Patient Baseline Laboratory Parameters, Secondary Objective	Baseline Assessment Period	Continuous	Electronic health records or physical patient file	(Albumin x BMI) (automatic calculation)
NT pro-BNP	Cardiac Red Flag, Functional Outcome, Secondary Objective	Baseline, Follow up Assessment Period	Continuous	Electronic health records or physical patient file	As recorded in the source data ng/L, (100-100000)
Troponin	Cardiac Red Flag, Functional Outcome, Secondary Objective	Baseline, Follow up Assessment Period	Continuous	Electronic health records or physical patient file	As recorded in the source data
Serum free light chain levels (Kappa) mg/L	Patient Baseline Laboratory Parameters, Secondary Objective	Baseline Assessment Period	Continuous	Electronic health records or physical patient file	As recorded in the source data mg/L, (5-1000)

Serum free light chain levels (Lambda) mg/L	Patient Baseline Laboratory Parameters, Secondary Objective	Baseline Assessment Period	Continuous	Electronic health records or physical patient file	As recorded in the source data mg/L, (5-1000)
Serum free light chain levels (Kappa/Lambda (automatic calculation))	Patient Baseline Laboratory Parameters, Secondary Objective	Baseline Assessment Period	Continuous	Electronic health records or physical patient file	free-kappa–lambda ratio (automatic calculation)
Serum immunofixation electrophoresis monoclonal gammopathy	Patient Baseline Laboratory Parameters, Secondary Objective	Baseline Assessment Period	Nominal	Electronic health records or physical patient file	As recorded in the source data yes/no
24h urine immunofixation monoclonal gammopathy	Patient Baseline Laboratory Parameters, Secondary Objective	Baseline Assessment Period	Nominal	Electronic health records or physical patient file	As recorded in the source data yes/no
Immunofixation/Immunoelectrophoresis monoclonal gammopathy	Patient Baseline Laboratory Parameters, Secondary Objective	Baseline Assessment Period	Nominal	Electronic health records or physical patient file	As recorded in the source data yes/no
Heart Rate	Patient Baseline ECG Parameters, Secondary Objective	Baseline Assessment Period	Discrete	Electronic health records or physical patient file	(BPM) Beat per minute, resting, as recorded in the source data
Rhythm	Patient Baseline ECG Parameters, Secondary Objective	Baseline Assessment Period	Nominal	Electronic health records or physical patient file	Heart rhythm 1-Normal Sinus Rhythm 2-Atrial Fibrillation
Pseudo infarct Sign	Cardiac Red Flag, Secondary Objective	Baseline Assessment Period	Nominal	Electronic health records or physical patient file	a Q-wave inversion on an electrocardiogram that mimics an

						acute myocardial infarction (present: Yes; or not: No)
Voltage Mismatch	Cardiac Red Flag, Secondary Objective	Baseline Assessment Period	Nominal	Electronic health records or physical patient file	Incompatibility between low QRS voltage on ECG and increased LV wall thickness on echocardiography (present: Yes; or not: No)	
Conduction Disturbance	Cardiac Red Flag, Secondary Objective	Baseline Assessment Period	Nominal	Electronic health records or physical patient file	The cardiac area refers to any abnormality in the electrical conduction system of the heart (present: Yes; or not: No)	
EF = Ejection Fraction	Patient Baseline Echo Parameters, Functional Outcome, Secondary Objective	Baseline, Index, Follow up Assessment Period	Continuous	Electronic health records or physical patient file	The percentage of blood that is ejected from the left ventricle of the heart with each contraction, as recorded in the source echocardiography data %	
IVS (Interventricular ar Septum)	Patient Baseline Echo Parameters, Functional Outcome, Secondary Objective	Baseline, Index, Follow up Assessment Period	Continuous	Electronic health records or physical patient file	The structure that separates the right and left ventricles of the heart, as recorded in the source echocardiography data mm	
LVEDD (Left ventricle end diastolic diameter)	Patient Baseline Echo Parameters, Secondary Objective	Baseline Assessment Period	Continuous	Electronic health records or physical patient file	The measurement of the diameter of the left ventricle at the end of diastole, as	

						recorded in the source echocardiography data mm
LVESD (Left ventricle end systolic diameter)	Patient Baseline Echo Parameters, Secondary Objective	Baseline Assessment Period	Continuous	Electronic health records or physical patient file	The measurement of the diameter of the left ventricle at the end of systole, as recorded in the source echocardiography data mm	
PW (posterior wall)	Patient Baseline Echo Parameters, Secondary Objective	Baseline Assessment Period	Continuous	Electronic health records or physical patient file	The thickness of the posterior wall of the left ventricle, measured during diastole, as recorded in the source echocardiography data mm	
LAVI (Left atrial volume index)	Patient Baseline Echo Parameters, Functional Outcome, Secondary Objective	Baseline, Index, Follow up Assessment Period	Continuous	Electronic health records or physical patient file	The volume of the left atrium normalized to body surface area, as recorded in the source echocardiography data mL/m ²	
LVMi (Left ventricle mass index)	Patient Baseline Echo Parameters, Secondary Objective	Baseline Assessment Period	Continuous	Electronic health records or physical patient file	The mass of the left ventricle normalized to body surface area, as recorded in the source echocardiography data mL/m ²	
E/A Ratio (Early to atrial)	Patient Baseline Echo	Baseline, Index,	Continuous	Electronic health records	The ratio of peak velocity blood	

filling velocity ratio)	Parameters, Functional Outcome, Secondary Objective	Follow up Assessment Period		or physical patient file	flow from left ventricular relaxation in early diastole to peak velocity flow in late diastole caused by atrial contraction, as recorded in the source echocardiography data
e' Lateral (mitral annulus wave)	Patient Baseline Echo Parameters, Secondary Objective	Baseline Assessment Period	Continuous	Electronic health records or physical patient file	The early diastolic velocity of the lateral mitral annulus, as recorded in the source echocardiography data mm/s
e' Septal (mitral annulus wave) mm/s	Patient Baseline Echo Parameters, Secondary Objective	Baseline Assessment Period	Continuous	Electronic health records or physical patient file	The early diastolic velocity of the septal mitral annulus, as recorded in the source echocardiography data mm/s
E/e' Lateral Ratio (Early mitral inflow velocity and mitral annular early diastolic velocity ratio)	Patient Baseline Echo Parameters, Secondary Objective	Baseline Assessment Period	Continuous	Electronic health records or physical patient file	The ratio of early mitral inflow velocity to the early diastolic velocity of the lateral mitral annulus, as recorded in the source echocardiography data
E/e' Septal Ratio (Early mitral inflow velocity and mitral annular early diastolic velocity ratio)	Patient Baseline Echo Parameters, Secondary Objective	Baseline Assessment Period	Continuous	Electronic health records or physical patient file	The ratio of early mitral inflow velocity to the early diastolic velocity of the

early diastolic velocity ratio)					septal mitral annulus, as recorded in the source echocardiography data
E/e' Mean Ratio (Early mitral inflow velocity and mitral annular early diastolic velocity ratio)	Patient Baseline Echo Parameters, Functional Outcome, Secondary Objective	Baseline, Index, Follow up Assessment Period	Continuous	Electronic health records or physical patient file	The average ratio of early mitral inflow velocity to the early diastolic velocity of the mitral annulus, as recorded in the source echocardiography data
Tricuspid Regurgitation Velocity	Patient Baseline Echo Parameters, Functional Outcome, Secondary Objective	Baseline, Index, Follow up Assessment Period	Continuous	Electronic health records or physical patient file	The peak velocity of blood flow through the tricuspid valve during regurgitation as recorded in the source echocardiography data m/s
Diastolic Dysfunction Stage	Patient Baseline Echo Parameters, Secondary Objective	Baseline Assessment Period	Ordinal	Electronic health records or physical patient file	The impairment of the heart's ability to relax and fill during diastole. It is typically graded based on echocardiographic findings (stage 1-2-3)
5-5-5 Findings	Patient Baseline Echo Parameters, Secondary Objective	Baseline Assessment Period	Nominal	Electronic health records or physical patient file	All e', a', s' velocities < 5 cm/s. This is a clue to the diagnosis of Cardiac Amyloidosis (present: Yes; or not: No)

TAPSE (Tricuspid Annular Plane Systolic Excursion)	Patient Baseline Echo Parameters, Functional Outcome, Secondary Objective	Baseline, Index, Follow up Assessment Period	Continuous	Electronic health records or physical patient file	The measurement of the displacement of the tricuspid annulus during systole, reflecting right ventricular function as recorded in the source echocardiography data mm
sPAP (Systolic Pulmonary Artery Pressure	Patient Baseline Echo Parameters, Secondary Objective	Baseline Assessment Period	Continuous	Electronic health records or physical patient file	Measurement of the pressure in the pulmonary artery during systole, as recorded in the source echocardiography data mmHg
Pericardial Effusion	Cardiac Red Flags, Secondary Objective	Baseline Assessment Period	Nominal	Electronic health records or physical patient file	Accumulation of fluid in the pericardial sac exceeding the physiological amount (present: Yes; or not: No)
Biatrial Dilatation	Patient Baseline Echo Parameters, Secondary Objective	Baseline Assessment Period	Nominal	Electronic health records or physical patient file	Enlargement of both atria, (present: Yes; or not: No)
Valve Thickening	Cardiac Red Flags, Secondary objective	Baseline Assessment Period	Nominal	Electronic health records or physical patient file	Increased thickness of heart valves, assessed via echocardiography (present: Yes; or not: No)
Tc99m PYP uptake; Perugini score	Patient Baseline Clinical Parameters,	Baseline Assessment Period	Ordinal	Electronic health records or physical patient file	Semi-quantitative visual scoring system for Tc99m PYP uptake, used

(PYP cardiac Scintigraphy Grade)	Secondary objective				to differentiate cardiac ATTR from AL amyloidosis (Grade 0-1-2-3)
Identification of hereditary vs. wild-type ATTR-CM (Wild - Variant)	Patient Baseline Clinical Parameters, Secondary objective	Baseline Assessment Period	Nominal	Electronic health records or physical patient file	Wild and Variant type of ATTR CM, this variable is defined by the TTR mutation test result, as recorded in the source data
TTR mutation variant (V30M, V122I, T60A, Ala81Thr, Arg34Gly, Other)	Patient Baseline Clinical Parameters, Secondary objective	Baseline Assessment Period	Nominal	Electronic health records or physical patient file	Mutation Type: V30M, V122I, T60A, Ala81Thr, Arg34Gly and other
6 min walking test m	Functional outcome, Secondary objective	Index, Follow up Assessment Period	Continuous	Electronic health records or physical patient file	Tests results as recorded in the source data
KCCQ Score per treatment (Kansas City Cardiomyopathy Questionnaire)	Functional outcome, Secondary objective	Index, Follow up Assessment Period	Ordinal	Electronic health records or physical patient file	Assessing physical limitations, symptoms, self-efficacy, social interference, and quality of life in heart failure patients.
Hospitalization due to CHF (Chronic Heart Failure)	Hospitalization data, Primary objective	Follow up Assessment Period	Nominal	Electronic health records or physical patient file	Admission to a hospital specifically for the treatment of Chronic Heart Failure will be recorded from electronic healthcare records through international classification system codes and assessment of

Admission to the emergency department due to CHF (present: Yes; or not: No)
	
Emergency admission data, Primary objective
	
Follow up Assessment Period
	
Nominal
	
Electronic health records or physical patient file
	
primary investigator, ICD codes in the EHR and assessment of the investigator will be used to classify the reason of hospitalization event as CHF, the ICD codes are defined at Section 9.3.1.

Cardiovascular related hospitalizations (present: Yes; or not: No)
	
Hospitalization data, Secondary objective
	
Follow up Assessment Period
	
Nominal
	
Electronic health records or physical patient file
	
Cardiovascular related hospitalizations will be recorded from electronic healthcare records through international classification system codes and

						assessment of primary investigator, ICD codes in the EHR and assessment of the investigator will be used to classify the reason of hospitalization event as cardiovascular related, the ICD codes are defined at Section 8.3.1 .
All-cause Mortality (present: Yes, date of event; or not: No)	Mortality data, Secondary objective	Follow up Assessment Period	Nominal	Electronic health records or physical patient file	Electronic health records or physical patient file	All-cause mortality including the date of the event (DD/MM/YYYY) will be recorded from electronic healthcare records
Tafamidis treatment prescription date	Primary and secondary objective	Index date	Continuous	Electronic health records or physical patient file	Electronic health records or physical patient file	The date on which the patient receives the prescription of Tafamidis as recorded in the patient's medical record. The start of Tafamidis treatment is expected shortly after the date of prescription. (DD/MM/YYYY)
Tafamidis treatment end date	Primary and secondary objective	Follow up assessment period	Continuous	Electronic health records or physical patient file	Electronic health records or physical patient file	The date on which a patient stops receiving Tafamidis treatment, recorded in the patient's medical records. (DD/MM/YYYY)

Any discontinuation of Tafamidis (Yes/No)	Primary and secondary objective	Follow up Assessment Period	Nominal	Electronic health records or physical patient file	The cessation of Tafamidis treatment for any reason (Yes/No)
Tafamidis discontinuation reason (1. Mortality, 2. Reimbursement rule, 3. Lost to follow up, 4. other)	Primary and secondary objective	Follow up Assessment Period	Ordinal	Electronic health records or physical patient file	Tafamidis Discontinuation Reason: (1. Mortality, 2. Reimbursement rule, 3. Lost to follow up, 4. other)

The dates of parameters obtained from tests such as ECG and echocardiography recorded at baseline, index, and follow-up dates will be entered into the eCRF system.

8.3.1. Definition of CHF-, CV - related hospitalizations and emergency admissions, and Red Flags

In our study, CHF and CV-related hospitalizations will be defined as following:

In this center and Turkish clinical practice, a **hospitalization or emergency admission due to chronic heart failure** is defined as an unplanned hospital admission due to worsening heart failure symptoms requiring intravenous diuretics, inotropic support, or other advanced heart failure therapies. In the electronic healthcare records international classification system codes (Version of ICD 10, such as I50 Heart Failure and its subcodes I50.1 Left ventricular failure, I50.2 Systolic Heart Failure, I50.3 Diastolic Heart Failure, I50.4 Combined Heart Failure, I50.8 Combined Heart Failure, etc.) for chronic heart failure hospitalization is defined and well recorded in this site. Emergency admissions for causes not related to chronic heart failure could not be accurately and completely captured; thus, these will not be recorded in CRF.

A **cardiovascular-related hospitalization** is defined as an unplanned hospital admission due to any cardiovascular event, in the electronic healthcare records international classification system codes such as I42 Cardiomyopathy, I44 Atrioventricular and left bundle branch block, I51 Complications and ill-defined descriptions of heart disease, I50 Heart Failure, etc.). The primary investigator is going to evaluate all cardiovascular and chronic heart failure related hospitalizations in terms of general practice in Turkey.

We identified specific **cardiac** and **extra-cardiac** symptoms and signs indicative of cardiac amyloidosis, which are classified as **red flags**. These were organized based on the guidelines from the “Diagnosis and Treatment of Cardiac Amyloidosis: A Position Statement of the European Society of Cardiology” (Garcia-Pavia P, Rapezzi C, Adler Y, et al. Diagnosis and treatment of cardiac amyloidosis: A position statement of the ESC Working Group on Myocardial and Pericardial Diseases. *Eur Heart J* -2021;42(16):1554–1568), some red flags mentioned in the position statement are not used or measured in daily clinical practice, therefore they are not planned to be included in the study.

Extra-cardiac Red Flags

- Carpal Tunnel Syndrome, Peripheral Neuropathy, Lumbar Stenosis, Renal Insufficiency (creatinine and GFR).

Cardiac Red Flags

- Elevated NT ProBNP and troponin, Pseudo infarct Sign, Voltage Mismatch, Conduction Disorder, Increased Wall Thickness (Interventricular septum), Pericardial Effusion.

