8.2. Setting

One Turkish Centre involved in the diagnosis and management of patients affected by ATTR-CM will participate in the study. This Centre is selected according to their clinical and research expertise, in

addition to the number of patients they are used to routinely caring for. A clinical research organization (CRO) on behalf of Pfizer will support the regulatory and administrative procedures to get authorization and the operations at Centre needed for data collection.

After regulatory authorization and local contract finalization, the study will be started at Centre. The site Study Team, including the Principal Investigator and additional identified personnel (e.g., research nurse, clinical study manager) will be trained on the protocol and planned study procedures, in addition to the use of the study-specific eCRF. Study data will be collected according to [Section 9.1. Study Design](#) and [Figure 1](#) as patients are diagnosed with ATTR-CM between January 2023 and January 2025. For all patients, the 6-month period before the index date when tafamidis is started will be considered as the baseline period, and the relevant parameters will be collected from this period. Original data, routinely collected by means of specific tools (e.g., paper charts, electronic charts,) will be transferred to the eCRF by the Study Team in site.

Retrospective data from the patient's files/source data will be collected in the CRF up to the earliest date of: treatment discontinuation, death, lost to follow-up (the patient could not be observed and any more contacted at some time point during their follow-up) or end of the follow-up period of 30-Sep-2025 (inclusive). For the patients lost to follow-up, the end of their follow-up period will be the respective date of the last contact. In the case patients experience clinical events (e.g. hospitalization due to Chronic Heart Failure, safety event) starting before 30-Sep-2025 and continuing beyond end of the follow-up, the respective details until the end of the event should be included into the eCRF.

The CRO will ensure oversight and monitoring of the study at the site.

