8.4. Data Sources

This is a retrospective study of existing healthcare data collected; no participants will be actively enrolled and there will be no collection of any primary data. All pseudonymized data will be entered/collected in a standardized case report form (CRF) designed specifically for this study. Data will be collected from individual patient medical records maintained in the Centre according to clinical practice in paper or electronic version. An electronic case report form (eCRF) will be utilized to ensure efficient data collection and management. Data collection will be performed by trained person who are familiar with the study protocol and the clinical data being collected. These individuals will be responsible for accurately entering the pseudonymized data into the eCRF.

The data collection process will involve reviewing patient medical records and extracting relevant information according to predefined criteria outlined in the study protocol. The pseudonymized data will be collected from site and will be processed for further analysis. For pseudonymization, each participant will have a specific code. Only the site investigators will be able to link the code with the participant.

Hospitalizations and emergency department visits due to CHF will be ascertained by the primary investigator using ICD codes and supporting hospital records. The primary investigator will verify that the event was primarily caused by chronic heart failure, based on the patients' history, laboratory results, and medications recorded in the discharge hospitalization or emergency summary form.

The validity of the recording and coding of the data will be ensured through several measures. First, the CRF will be designed to capture standardized clinical information, reducing variability in data entry. Second, the study site team responsible for data collection will undergo training to ensure consistency and accuracy in data abstraction. Third, quality review by CRO will be conducted to verify the accuracy and completeness of the recorded data.

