8.7. Data Analysis

The anonymously collected data of each patient cohort will be analyzed with an exploratory data analysis approach. The de-identified dataset will be analyzed using statistical software. Descriptive

statistics, survival analyses, and exploratory methods will be employed to address study objectives. Outliers and data inconsistencies will be reviewed and addressed before final analysis. Only descriptive statistics will be reported and no effort to determine statistical significance will be made.

Hospitalization and emergency department admission rates attributable to chronic heart failure, as well as hospitalization rates for cardiovascular-related illness, will be expressed as events per patient-year to account for variable follow-up durations.

Overall survival will be described using the Kaplan–Meier method, appropriately accounting for differing follow-up times and censoring; competing risks will not be considered.

Cardiac and extra-cardiac “red flags,” together with clinical and functional outcomes, will be described using means (standard deviations) for continuous variables and proportions for categorical variables.

Missing data will not be imputed; all analyses will be based on available data, with the number of missing observations reported for each variable where applicable.

Detailed methodology for summary and statistical analyses of data collected in this study will be documented in a statistical analysis plan (SAP), which will be dated, filed, and maintained by the sponsor. The SAP may modify the plans outlined in the protocol; any major modifications of primary endpoint definitions or their analyses would be reflected in a protocol amendment.

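### Table 1 lists the CHF and CV admissions as nominal variables with no date or count, which does not fit the events-per-patient-year analysis in section 8.7

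*Protocol*

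**What the plan says.** The primary objective (section 7) is the rate of hospitalizations and emergency admissions due to chronic heart failure. Section 8.7 says that these rates, and the rate of cardiovascular hospitalization, "will be expressed as events per patient-year to account for variable follow-up durations".

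Table 1 (section 8.3) gives the variables behind those rates:

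- "Hospitalization due to CHF (Chronic Heart Failure": output type Nominal, with no yes/no label in the row name.
- "Admission to the emergency department due to CHF (present: Yes; or not: No": output type Nominal, yes/no.
- "Cardiovascular related hospitalizations (present: Yes; or not: No": output type Nominal, yes/no.
- "All-cause Mortality (present: Yes, date of event; or not: No": output type Nominal, with a date.

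None of the three admission rows shows an event date or a number of events. The sentence below the table on dates in the eCRF reads "The dates of parameters obtained from tests such as ECG and echocardiography" and does not name admissions.

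Other sections point towards records of single events. For an event that starts before 30 September 2025 and runs on, section 8.2 says "the respective details until the end of the event should be included into the eCRF". Section 8.4 says "The primary investigator will verify that the event was primarily caused by chronic heart failure". Section 8.9 says that every cardiovascular hospitalization is to be entered in the CRF.

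**The concern.** The numerator of an events-per-patient-year rate is a count. A yes/no flag cannot supply it once a patient has a second admission, and repeat admissions are to be expected in heart failure. A flag divided by full follow-up is not a first-event rate either, because person-time for a first event has to stop on the event date.

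Dates are also needed to decide which events belong in the numerator. Section 8.2 ends follow-up at the earliest of stopping treatment, death, loss to follow-up or 30 September 2025. An undated admission cannot be checked against that window.

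The SAP can define a numerator, but it cannot supply data that were never abstracted. Section 8.4 ties abstraction to criteria set out in the protocol, and section 8.8 limits collection to what the objectives need and uses Table 1 as a reference for data checks. Section 5 gives 16 October 2025 as the start of data collection and 30 June 2026 as its end, so a late correction could mean opening the charts again.

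**Working it through.** The protocol states no expected rate, event count or dispersion, so there is no figure of its own to reproduce. The check asks how far the reported rate would fall short under each reading of Table 1.

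**Inputs from the protocol**
- About 70 patients (section 8.2).
- Follow-up of roughly 6 to 30 months (given as a reason in the amendment table, section 4; used here for illustration only).
- Quarterly follow-up (section 8.1).

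**Assumptions**
- Follow-up T is uniform on 0.5 to 2.5 years, with mean 1.5, so 70 × 1.5 = 105 patient-years.
- The true rate L is 0.2 to 0.5 per patient-year.
- Events are either Poisson, or clustered in patients through a gamma-distributed patient rate with shape k = 0.5.

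**Formulas for the reported rate**
- Every event entered: L.
- One flag per patient, Poisson: E[1 − exp(−LT)] / E[T].
- One flag per patient, clustered: E[1 − (1 + LT/k)^(−k)] / E[T].
- One flag per quarter, Poisson: (1 − exp(−L/4)) / 0.25.
- One flag per quarter, clustered: (1 − (1 + 0.25L/k)^(−k)) / 0.25.

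**Worked case, L = 0.5, one flag per patient**
- Poisson: E[exp(−LT)] = (e^−0.25 − e^−1.25) / (0.5 × 2) = 0.7788 − 0.2865 = 0.4923. The reported rate is (1 − 0.4923) / 1.5 = 0.338, which is 32% too low.
- Clustered: with k = 0.5, E[(1 + T)^−0.5] = √3.5 − √1.5 = 1.8708 − 1.2247 = 0.6461. The reported rate is (1 − 0.6461) / 1.5 = 0.236, which is 53% too low.

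**Understatement of the rate**

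| True rate L | Expected events in 105 patient-years | One flag per patient, Poisson | One flag per patient, clustered | One flag per quarter, Poisson | One flag per quarter, clustered | Every event entered |
|---|---|---|---|---|---|---|
| 0.2 | 21.0 | 15.3% | 32.3% | 2.5% | 6.9% | 0% |
| 0.3 | 31.5 | 21.6% | 41.1% | 3.7% | 10.0% | 0% |
| 0.5 | 52.5 | 32.3% | 52.8% | 6.0% | 15.5% | 0% |

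The flags always push the rate down. The table covers uncounted repeat events only. The effect of undated events that fall outside the follow-up window is not quantified, because nothing in the protocol indicates how many there might be.

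**The case against.** The strongest reply is that Table 1 is a list of variables and not the eCRF specification, and that the rest of the protocol reads as event-level capture. The extension past the cut-off in section 8.2 makes sense only if events have a start and an end. In section 8.3.1 the investigator evaluates all heart failure and cardiovascular hospitalizations, in section 8.4 the cause of an event is verified, and section 8.9 has all cardiovascular hospitalizations recorded. On that reading Nominal could describe an attribute of each event (caused by heart failure or not), and section 8.7 already fixes the rate. The study is retrospective, so the source records remain available.

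Much of this stands. A reader might infer from Table 1 that repeat admissions will be lost, or that the primary analysis cannot be done. The documents do not support that: no section keeps only one event per patient, and the outcome depends on how the eCRF is built. Nor is the whole primary outcome a yes/no variable, since the heart failure hospitalization row has no such label. The definition cell of the emergency row is broken in the extracted table text, so the absence of a date there is less certain than in the cardiovascular row, which is complete.

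The contradiction remains. Section 8.2 presupposes start and end dates that Table 1 does not list, section 8.4 concerns the cause of an event and not its date or number, and no section says that each event's date or the number of events is recorded.

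**Conclusion.** The point holds as an inconsistency in how the primary variables are specified. The admission rows of Table 1 do not match the rate in section 8.7 or the event-level language in sections 8.2, 8.4 and 8.9.

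The harm is conditional. If Table 1 were applied with one flag per patient, the rate would be understated by about 15 to 32% under Poisson and 32 to 53% with clustering at shape 0.5. With one flag per quarter the shortfall would be about 2.5 to 6% and 7 to 15.5% respectively. If every event is entered there is none. These figures rest on assumed rates, an assumed dispersion and uniform follow-up, none of which the protocol gives. They show the direction and rough size and do not predict the study's result. It deserves correction because it concerns the only primary objective, the error would flatter outcomes on treatment, and the remedy is cheap while data entry is still open.

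**What to change.** In Table 1, replace the three admission rows with one repeating record per qualifying admission: type (heart failure hospitalization, heart failure emergency admission, cardiovascular hospitalization), admission date, discharge date, ICD code and the investigator's classification.

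State beside it, or in section 8.7, that the numerator is all qualifying events starting between the index date and the end of follow-up, and that the denominator is the sum of that time over patients. The dates would also let the SAP say how to count an emergency visit that leads to a hospitalization.

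If the eCRF already holds one dated record per event, the cost is an edit to Table 1. If not, it also needs a repeating form and a second look at patients already entered. The investigator already reviews the discharge or emergency summaries to classify cause (section 8.4), so the dates should be at hand.
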